2. Compare the effects of the intervention vs. enhanced usual-care control on secondary outcomes, including short- and long-term changes in diabetes and prediabetes-related outcomes of metabolic markers of glycemic control (a) hemoglobin A1c, and (b) fasting glucose; cardiovascular disease risk factors: (c) fasting lipid profile; and lifestyle outcomes: (d) dietary intake (total energy, simple carbohydrates, saturated fat, number of servings of fruits and vegetables, dietary fibers, and whole grains), and physical activity.
3. Determine the implementation cost of delivering this weight-loss intervention at a Federally Qualified Health Center in the context of a pragmatic clinical trial.

Research Design

This will be a randomized clinical trial testing a weight-loss lifestyle intervention for obese Hispanic women with prediabetes or T2D. The primary aims of the intervention will be to reduce body weight and waist circumference at 6, 12, and 18 months. Secondary aims will be to improve levels of HbA1c, markers of glycemic control (fasting glucose in addition to HbA1c) and cardiovascular disease risk (serum lipid profile), diet, and physical activity. We will also determine the implementation cost for delivering the trial intervention in a federally qualified health center. Following the clinical trial, through a 2-cohort phase, we will assess the sustainability and cost of delivering the intervention as part of regular patient care at the clinic in the absence of research support.

Trial participants will be randomly assigned to one of two conditions: 1) Enhanced usual care control, or 2) a culturally tailored behavioral intervention. Outcome assessments will be conducted at 6, 12, and 18 months. Recruitment will be conducted in seven cohorts of approximately 30 randomized participants each.

Each participant will receive a \$25 gift card at the completion of the 6-month visit, \$30 at 12-month and \$35 at 18-month data collection points.

Eligibility

We will enroll 200 obese Hispanic women in this weight-loss intervention trial.

Inclusion criteria.

- All participants will be patients who receive their primary medical care at the Virginia Garcia Memorial Health Center (VGMHC)
- Self-identified as Spanish-speaking Latina or Hispanic
- Female
- Age 18 and older
- BMI greater than or equal to 27kg/m²
- Classified as diabetic or prediabetic in the electronic medical record by *at least one* of the following:
 - o Fasting plasma glucose ≥ 100

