Bathroom Scale: As found in other studies,³⁸ our research experience has been that few Hispanic women self-weigh regularly, and most do not own a scale. To aid in self-monitoring, all participants will be provided with a digital bathroom scale.

Pedometer: A pedometer and printed bilingual instructions for its use and tips for increasing PA will be provided to help participants monitor daily steps. We will not use pedometers for outcome data collection.

Measuring cups and spoons: Our pilot work has shown that many Hispanic women are unfamiliar with Anglo-American food measurements.¹⁴ Traditional Latin American cooking practices rarely use measuring cups and spoons. To help participants measure their food, all participants will be provided with a set of measuring cups and spoons, along with a printed equivalence table (Anglo-American measuring units and metric units).

Retention

To maximize participant retention, during the screening process will we provide oral and written information about study expectations, time commitment, schedule and length of intervention group sessions, and potential benefits and risks. To enhance completion of the assessment visits, we will use appointment reminders (letters and phone), and schedule visits at times as convenient as possible to the participant.

Weight Loss Intervention

The initial intervention will consist of weekly meetings for 6 months, as recommended by Wadden.⁹³ The meetings will be structured to be very interactive, involve participant input and group activities, foster problem solving, support, and program ownership. We are planning for approximately 15 participants per group; groups of similar size have been shown to be quite effective in previous weight-loss studies.^{3,25}

Each session will have a similar structure with 6 main components:

1. Social support/group sharing
2. Review of each individual's progress since the last session
3. Main content area (e.g., meal patterns, calories)
4. Behavioral skills training
5. Goal setting and action plans (in small groups)
6. Plans of self-monitoring activity

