After the completion of the first six months of weekly intervention sessions, participants will attend monthly group sessions and will also interact with each other weekly by telephone. The monthly group sessions and weekly telephone contacts constitute a weight-maintenance phase which will help maintain self-management behaviors started during the initial intervention. The self-management behaviors include setting weekly behavioral goals and developing specific action plans to achieve those goals, social disclosure of these goals and plans, and scheduled accountability for evaluating the outcomes of these plans.

The structure of these monthly, one hour and-a-half group sessions of the maintenance phase will be similar to the initial weight loss sessions, starting with a weigh-in and reporting to the group regarding the outcome of their weight management efforts since the last group session. The session leaders will then lead a discussion focused on a selected self-management strategy such as environmental modification, stimulus control, or social contracting, with illustrations taken from the participants' experience. There will also be a presentation on a topic recommended by participants at previous meetings, emphasizing managing ongoing challenges of making appropriate food choices and managing total energy intake, motivation, and resistance training.

Motivation for attending the monthly group sessions are social support from other group members, new information on nutrition presented by group leaders, and advice from peers and group leaders. The importance of attending the monthly maintenance meetings will be emphasized during the final 4 weekly weight-loss sessions with encouragement for participants to make a commitment to the group to return to the monthly meetings.

Participants will be asked to establish a telephone support net for which each participant will call one other participant between group meetings. This telephone contact, which will be promoted as a transition aide and as an essential part of the weight-loss maintenance program, will be introduced 2 weeks before the end of the weekly sessions. Participants will be encouraged to contact each other according to a mutually agreed upon schedule for brief (5-10 minute) supportive telephone conversations. The network will provide ongoing social support between the monthly group sessions.

Dietary, Exercise and Behavioral Recommendations

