The main analysis will be based on intention-to-treat principles. To test the effect of the intervention on the short term outcomes at 6 months, we will use a residualized change score to determine whether the intervention and control groups differ in change in outcome (e.g., weight and HbA1c) from baseline, controlling for baseline values. The analysis uses regression with the dependent variable being the change in weight (or HbA1c) at 6 months and the independent variables are baseline weight (or HbA1c) and a dummy variable for study arm (intervention versus control). To examine the long-term effect of the intervention we will use multilevel modeling to examine the trajectory of the outcomes across baseline, 6, 12, and 18 months. Weight (or HbA1c) is the dependent variable; time, study arm, and the time by study arm interaction are the independent variables. Quadratic models will be fit to the data, as it is anticipated that the change over time will not be linear throughout the 18 month period. These approaches will also be used for the analysis of the short-term and long-term effects of the intervention on other outcomes: waist circumference, fasting glucose, serum lipid profile, dietary intake (total energy, simple carbohydrates, saturated fat, number of servings of fruits and vegetables, dietary fiber and whole grains), and PA.

Assessment of success in sustainability phase

To evaluate the success of the implementation of the intervention into clinical practice at VGMHC, the average percentage of behavioral strategies, participant objectives, session content completed across sessions, average number of participants recruited, average participant satisfaction, percent of sessions attended in each phase, and average weight change will be reported. These numbers will be compared to the benchmark numbers established during the clinical trial phase of the study.

Additional Analyses

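### Only intervention women are treated in groups of about 15, but the 6-month regression has no group term; if group effects vary, that omission makes its standard error too small, by an amount that depends on an ICC the documents do not give

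*Combined protocol and SAP*

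**What the plan says.** All references are to the combined protocol and SAP.

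- **Research Design:** "The primary aims of the intervention will be to reduce body weight and waist circumference at 6, 12, and 18 months". Also: "Recruitment will be conducted in seven cohorts of approximately 30 randomized participants each".
- **Eligibility:** "We will enroll 200 obese Hispanic women in this weight-loss intervention trial".
- **Baseline Data Collection and Randomization:** women are allocated individually in blocks of 4 with equal arms, stratified by BMI (three bands) and age (two bands).
- **Weight Loss Intervention:** intervention women meet weekly for six months. "The meetings will be structured to be very interactive, involve participant input and group activities", and "We are planning for approximately 15 participants per group". In the maintenance phase that follows, "participants will attend monthly group sessions and will also interact with each other weekly by telephone".
- **Recruitment and Enhanced Usual Care Control:** controls receive printed materials and the tools given to both arms. No control sessions are described.
- **Statistical Analysis, 6 months:** change is regressed on two terms: "the independent variables are baseline weight (or HbA1c) and a dummy variable for study arm (intervention versus control").
- **Statistical Analysis, long term:** in a multilevel model with quadratic time, "time, study arm, and the time by study arm interaction are the independent variables".

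The same approaches are extended to waist circumference and the secondary outcomes. No group term, cluster-robust variance, ICC or design effect appears anywhere.

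**The concern.** The programme is meant to work partly through the group: shared sessions, peer support and calls between members. Women in one group may therefore have correlated outcomes at 6, 12 and 18 months. Controls have no such structure, so the clustering is in one arm only.

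The 6-month regression treats all women as independent. If groups differ in how well they do, the arm comparison carries a variance component that the regression ignores. This can happen even when the average effect is zero. Its intervals would then be too narrow, and false positives more frequent than the nominal rate, for weight and waist (both in the primary aims) and for any other outcome whose own ICC is positive.

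**Working it through.** The plan gives no sample-size calculation, alpha or ICC, so there is no figure of its own to reproduce.

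**Inputs from the documents.** 200 women and equal arms give about 100 per arm. Seven cohorts of about 30, split equally, give about 15 intervention women per cohort. That matches the planned group size, so about seven groups are inferred; the number is not stated. Average group size is m = 100/7 = 14.3.

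**Assumptions.** Two-sided 5% test; ICC from 0 to 0.10; equal total variance in both arms. The 20% loss and the shared cohort ICCs used below are also assumed.

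**Step 1: size of the group effect alone.** With clustering in one arm and equal allocation, the true variance of the arm difference divided by the variance the regression assumes is about

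VI = [1 + (1 + (m − 1) × ICC)] / 2,

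and the type I error is 2 × (1 − Φ(1.96/√VI)).

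Example at ICC 0.05: VI = (2 + 13.3 × 0.05)/2 = 1.332, √VI = 1.154, 1.96/1.154 = 1.70, giving 9.0%.

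| ICC | VI | Formula, complete data | Simulated, complete data | Formula, 20% loss (m = 80/7 = 11.4) | Simulated, shared cohort ICC 0.05 |
|---|---|---|---|---|---|
| 0 | 1.000 | 5.0% | 5.0% | 5.0% | 4.3% |
| 0.01 | 1.066 | 5.8% | 5.7% | 5.6% | 5.4% |
| 0.02 | 1.133 | 6.6% | 6.7% | 6.2% | 5.8% |
| 0.05 | 1.332 | 9.0% | 9.3% | 8.1% | 8.5% |
| 0.10 | 1.664 | 12.9% | 13.0% | 11.2% | 12.4% |

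The simulations used 20,000 null trials per cell (Monte Carlo standard error about 0.15 to 0.24 points). The last column has complete follow-up.

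**Step 2: the offset from cohorts.** Each cohort supplies both arms, so a cohort effect shared by both arms cancels from the arm difference. It still inflates the residual variance of a model that omits cohort. With n women per arm, residual variance σ², group variance g and cohort variance c:

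- true variance ≈ (2σ² + m g)/n
- variance assumed by the regression ≈ (2σ² + 2c + g)/n

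The net standard error is too small only if (m − 1) g > 2c. At m = 14.3 the balance point is c = 6.6 g (13.3/2). At group ICC 0.01 that is a cohort ICC near 0.07; at group ICC 0.05 it is near 0.33. Simulation agrees. At group ICC 0.01 the type I error is 4.8% with a shared cohort ICC of 0.10 and about 4.5% with 0.15. At group ICC 0.05 or more it stayed above 5% for every shared cohort ICC tested, up to 0.15.

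**Step 3: power.** A standardised effect of 0.396 has 80% power with 100 independent women per arm. It is illustrative, since the plan states no target. The power of a valid test with known variance is Φ(0.396/√(2 × VI/100) − 1.96). The model with a random group effect and no cohort term was simulated with REML and Satterthwaite degrees of freedom (2,000 trials per cell, Monte Carlo standard error about 1.1 points for power).

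| ICC | Valid test, known variance | Model with group effect |
|---|---|---|
| 0 | 80% | 73% |
| 0.02 | 75% | 67% |
| 0.05 | 68% | 62% |
| 0.10 | 58% | 51% |

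At ICC 0.10, 22 of the 29 points lost come from the clustering itself; at 0.05, 12 of 18. At ICC 0 all 7 points are the cost of the fix.

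**The case against.** **The ICC may be negligible.** This stands as a limit on size. At ICC 0 the test is correct, and at 0.01 the excess is under 1 point. Nothing in the documents says where the ICC lies, and the plan as written would not estimate it.

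**Other omissions push the other way.** This also stands. Shared cohort effects can make the net test slightly conservative at group ICC 0.01. The age and BMI strata used in randomisation are absent from the model too; if they predict weight change, that also makes the standard error too large. I did not compute the size of the strata effect. A reader might infer that the planned standard error is bound to be too small. The documents do not support that: the sign is clear for the group component, not for the net result at small ICCs.

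**The long-term model is already multilevel.** A reader might infer that it definitely ignores groups. The text does not say so: a group level is neither stated nor excluded. Repeated measures within women would satisfy the wording, so the gap is one of specification. The size of any error there was not computed.

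**Inference could be limited to these groups.** The inflation concerns inference beyond the particular groups formed, and the plan states no such target. But it describes a programme meant to be sustained and disseminated, followed by a sustainability phase with new cohorts, which points to the wider inference.

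The planned data audit covers quality, completeness, outliers and distributions; it does not mention independence.

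**Conclusion.** The concern holds in conditional form and should be fixed. The 6-month regression leaves out a source of correlation that the design creates in one arm. If group effects vary, that omission makes the standard error too small. Under the stated assumptions, with complete follow-up and no shared cohort effects, type I error runs from 5.8% at ICC 0.01 to 12.9% at ICC 0.10.

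At ICC 0.05 or more the test stayed anti-conservative in every cohort scenario tested. At ICC 0.01 the net error may be nil or reversed. Confidence is medium, because the ICC, the alpha, the loss rate and the shared cohort variance are all assumed and the number of groups is inferred.

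**What to change.** - Carry an intervention-group identifier into the analysis dataset, using the group each woman was assigned to whether or not she attended.
- In the 6-month model, and explicitly in the long-term model, add a random effect for intervention group in the intervention arm only (each control as a singleton), with arm-specific residual variance and small-sample degrees of freedom.
- State in advance how degrees of freedom are set when the group variance is estimated as zero. With about seven groups this will be common: 57%, 48%, 41%, 25% and 12% of simulated null trials at ICC 0, 0.01, 0.02, 0.05 and 0.10. The choice matters: at ICC 0, power was 73% with the zero component dropped from the degrees of freedom and 63% with it kept.
- Have the trial statistician pre-specify whether the primary model has a cohort term, and run the other version as a sensitivity analysis. The simulations do not settle it. With shared cohort effects (ICC 0.05), type I error was 2.0% to 4.5% without the term and 3.1% to 4.6% with it. Power at ICC 0 was 65% and 67%, a gap within simulation error.
- Report the estimated ICC.

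The cost is SAP wording and one variable, with no added patients or procedures. The price is wider intervals and the loss of power shown in the working.

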The change in consent will affect about 90 participants. Participants in the intervention groups will receive their new consent at one of the sessions. Usual care participants will receive a phone call from [name] alerting them to watch for the form in the and if desired discuss the change in the consent.

Prior to randomization, participants will be required to obtain medical clearance for participation from their VGMHC health care provider.

Baseline Data Collection and Randomization

After completing the baseline telephone assessments, participants will be scheduled for a randomization visit at VGMHC. During this visit we will collect baseline measurement of fasting lipids, glucose, and HbA1c as they are done in the course of clinic operations at VGMHC, by

finger-stick using point-of-care devices. Participants will then receive their treatment assignments using a computerized block randomization scheme provided by the study statistician. Randomization will be stratified by baseline BMI (27-34, 35-39, 40 or more) and age (18-45, 46 and above). To ensure equal balance in the two arms, randomization will occur in block sizes of 4. Participants will be informed of their randomization assignments by intervention staff members. Data collection staff will be masked to treatment assignments.

Enhanced Usual Care Control

We considered using a no-treatment control condition, but our community clinic partners requested that we provide the same information to participants in both conditions. This strategy insures that all participants get something they value as part of their involvement in the study, and also provides a comparison of the lifestyle intervention program to a very low-cost and easy to deliver information-only program.

Weight Management Tools for All Trial Participants

So that all randomized participants receive the same basic information, those assigned to the enhanced usual care control condition will receive bilingual printed materials on how to improve weight-related behaviors: copies of the NHLBI “Steps to Lose Weight,” “ChooseMyPlate,” and “Nutrition and Finding Your Way to a Healthier You.” We recognize that literacy limitations may be an issue for some participants, but providing this type of printed material is our approximation of the best current “usual care” practice. In addition to this written material, all participants in both arms of the trial will receive:

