The weight loss program is designed to achieve weight loss through dietary calorie reduction, increased energy expenditure through physical activity, and improved self-efficacy through behavioral self-management.

Dietary recommendations:

1. Consume ~500 fewer calories per day to achieve ½-2 lb weight loss per week.
2. Eat a healthy dietary pattern (i.e., the DASH eating style and WLM program, a diet rich in fruits, vegetables, and low-fat dairy foods, and low in fat).
3. Limit alcohol consumption to no more than one drink per day.

Physical activity recommendations:

4. In addition to normal daily activities, exercise at moderate intensity most days per week.
5. Progress gradually to 30-60 minutes/day to a weekly target of at least 180 minutes.

Behavioral recommendations:

6. Record daily food intake and physical activity.
7. Set short-term goals and create action plans.
8. Be an active study participant by attending intervention group sessions.

Measures

Weight will be measured with participants in light indoor clothes without shoes, and determined to the nearest 0.1 kg by a calibrated digital scale.

Height will be measured at enrollment to the nearest 0.1 cm using a calibrated, wall-mounted stadiometer.

Waist circumference will be measured at the midpoint between the lower rib and the iliac crest. We will record this to the nearest 0.5 cm. Measurement will be done with a Linen non-stretch tape measure with a tension device to provide a constant tension during measurement.

HbA1c and fasting lipids, and glucose will be collected in the course of patient care, using point-of-care devices to facilitate data collection by VGMHC staff members. Data will be collected for all trial participants at baseline, 6-, 12-, and 18-months post randomization. For participants that are unable to come to the clinic for the blood draw, we will do a home outreach and collect the sample at their homes.

Fasting lipids (total cholesterol, HDL-cholesterol, and triglycerides) will be measured enzymatically (Lipid Panel Plus Reagent Disc; Henry Schein, Inc, Melville, NY) in whole blood using a Piccolo Blood Chemistry Analyzer (Abaxis Inc., Union City, CA). LDL-cholesterol will be calculated using the Friedewald equation.⁹⁶ Fasting

glucose will be measured using a OneTouch Ultra blood glucose monitoring system (LifeScan, Inc. Milpitas, CA). HbA1c will be measured from capillary blood using an A1cNow+ device (Bayer HealthCare LLC,

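### The 6-month fasting-glucose regression is valid but leaves out baseline HbA1c, already collected at the same visit; adding it would probably gain a little precision (about 1-4% of residual variance under assumed inputs)

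*Combined protocol and SAP*

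**What the plan says.** The Statistical Analysis section defines the 6-month analysis as a regression of change from baseline in which "the independent variables are baseline weight (or HbA1c) and a dummy variable for study arm (intervention versus control". It then widens the scope: "These approaches will also be used for the analysis of the short-term and long-term effects of the intervention on other outcomes: waist circumference, fasting glucose". Read together, these give a fasting-glucose model with two terms, baseline glucose and arm. No other covariate is added, apart from health literacy, numeracy and acculturation in the moderator analyses under Additional Analyses.

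The long-term model is different: "Weight (or HbA1c) is the dependent variable; time, study arm, and the time by study arm interaction are the independent variables". There, baseline is one point on the trajectory and not a covariate.

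On the data, Baseline Data Collection and Randomization says "During this visit we will collect baseline measurement of fasting lipids, glucose, and HbA1c", by "finger-stick using point-of-care devices", and participants receive their assignment after that. The Measures section says "glucose will be measured using a OneTouch Ultra blood glucose monitoring system"; it describes no replicate reading and measures HbA1c on a separate device. Both markers are secondary outcomes under Aim 2: "metabolic markers of glycemic control (a) hemoglobin A1c, and (b) fasting glucose".

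**The concern.** A single capillary fasting glucose reflects usual glycaemia only in part, because it carries day-to-day variation and meter error. HbA1c, measured on another device, reflects the same underlying state with error that is plausibly separate. Leaving it out of the glucose model leaves in the residual some between-woman variation that could be explained.

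Two features of the trial make this worth a look. Eligibility runs from prediabetes to diagnosed diabetes, so baseline glycaemia should vary widely. Randomization is stratified by BMI and age only, so nothing in the design balances the arms on glycaemic status. At stake is a somewhat wider confidence interval for the 6-month glucose comparison than the collected data require.

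**Working it through.** **Plan's own figure.** There is none to reproduce. The enrolment target of 200 is given without alpha, power, effect size or SD, and no SD, reliability or correlation is given for either marker. Every input below except N = 200 is an assumption.

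**Assumed inputs.** S = SD of true fasting glucose, 25-50 mg/dL. e = SD of day-to-day plus meter noise, 10-25 mg/dL. r = correlation of measured HbA1c with true glucose, 0.5-0.8. d = SD of true 6-month change, 20-30 mg/dL, taken as unrelated to baseline.

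**Formulas.**
- Uncertainty about true baseline given the reading alone: V1 = 1/(1/S² + 1/e²).
- Given the reading and HbA1c: V2 = 1/(1/(S²(1 − r²)) + 1/e²).
- Residual variance of the 6-month comparison: d² + e² + V1 as planned, and d² + e² + V2 with HbA1c added.

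**Middle case, S = 40, e = 15, r = 0.8.**
- V1 = 1/(1/1600 + 1/225) = 197.3.
- V2 = 1/(1/576 + 1/225) = 161.8.
- d = 20: 400 + 225 + 197.3 = 822.3 falls to 786.8, a reduction of 4.3%.
- d = 30: 900 + 225 + 197.3 = 1322.3 falls to 1286.8, a reduction of 2.7%.

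**Same S and e, varying r.**

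| r | V2 | Reduction, d = 30 | Reduction, d = 20 |
|---|---|---|---|
| 0.8 | 161.8 | 2.7% | 4.3% |
| 0.7 | 176.4 | 1.6% | 2.5% |
| 0.6 | 184.5 | 1.0% | 1.6% |
| 0.5 | 189.5 | 0.6% | 0.9% |

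For r of 0.6-0.8 this is 1.0% to 4.3%. In women, 200 × (1322.3/1309.5 − 1) ≈ 2 and 200 × (822.3/786.8 − 1) ≈ 9. The largest of these reductions shortens the standard error by 1 − √(786.8/822.3) ≈ 2.2%.

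**Ends of the range.**
- Low: S = 50, e = 10, r = 0.5, d = 30. V1 = 96.2, V2 = 94.9; 1096.2 falls to 1094.9, or 0.1%.
- High: S = 25, e = 25, r = 0.8, d = 20. V1 = 312.5, V2 = 165.4; 1337.5 falls to 1190.4, or 11.0%, about 25 women.

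**Cost of the covariate.** One degree of freedom at n = 200 inflates the variance by about (200 − 4)/(200 − 5) = 1.005, or 0.5%.

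**Cross-check by correlations.** Let a = correlation of the 6-month value with its own baseline, b = with the other marker's baseline, and c = between the two baselines. R² rises from a² to (a² + b² − 2abc)/(1 − c²), and the gain is nil when b = a × c.
- Glucose outcome, (a, b, c) = (0.6, 0.6, 0.7): R² goes from 0.36 to 0.424, so variance falls by 1 − 0.576/0.64 = 9.9%.
- (0.6, 0.5, 0.7): 2.0%. (0.7, 0.5, 0.7): about 0%. (0.5, 0.6, 0.7), where HbA1c predicts later glucose better than baseline glucose does: 16.3%.
- Simulation with 200 women and 4000 replicates gave variance ratios of 0.909, 0.985 and 1.007 for the first three, so at break-even the covariate costs slightly more than it returns.

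**Reverse case, HbA1c outcome with baseline glucose added.** (0.7, 0.6, 0.7): 4.7%. (0.8, 0.65, 0.7): 4.4%. (0.8, 0.6, 0.7): 0.9%. (0.85, 0.6, 0.7): 0.02%.

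**Long-term model.** A time-invariant covariate entered as a main effect explains between-woman differences in level, whereas the arm effect lies in the time-by-arm terms. In simulated complete data (200 women, four visits, quadratic time, random intercept and slope, 40 replicates), adding baseline HbA1c changed the time-by-arm estimate by at most 1e-12, and the standard-error ratio was 1.000000.

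**The case against.** The strongest reply is that nothing here is wrong. Change regressed on own baseline and arm gives the same arm effect as analysis of covariance on the 6-month value; it is valid under randomization and already uses the most natural covariate. Many outcome models could be criticised for omitting some correlated baseline. Fasting glucose is secondary, and no power claim is made for it. All of that stands, and it confines the point to an optional gain in efficiency.

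The size also rests on inputs absent from the documents. HbA1c here is itself a capillary point-of-care value, so a correlation of 0.8 is not a cautious single choice; lower values shrink the gain towards the cost of the degree of freedom. That stands, which is why r is varied above. In the measurement-error model, however, any noise in the glucose reading leaves HbA1c something to add. The near-zero glucose cases need a very reliable single reading: a × c/b is 0.96 at (0.6, 0.5, 0.8) and 0.98 at (0.7, 0.5, 0.7).

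The change is not free of risk either. If women without a baseline HbA1c were dropped, losing 3% of them would raise the variance by 1/0.97 − 1 = 3.1%, enough to cancel much or all of the usual gain. This is met by an imputation rule.

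A reader might infer that the same omission weakens the HbA1c model equally and the 12- and 18-month analysis too. Neither follows: HbA1c probably tracks itself well enough for glucose to add little, and the long-term model has no baseline covariate to supplement.

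**Conclusion.** The point holds as a minor, optional improvement to the 6-month fasting-glucose regression. The documents establish that the model uses baseline glucose and arm only, and that baseline HbA1c is collected at the same visit before assignment. They do not establish that precision is lost. That is a plausible inference: about 0-11% of residual variance over the assumed ranges, and 1-4% in the middle case with correlations of 0.6-0.8, before the 0.5% cost. The correlation route gives 0-16%, its top value needing HbA1c to out-predict baseline glucose. The mg/dL range is preferred because its inputs can be judged directly, but neither can be confirmed from the documents.

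A reader might take this to mean that the planned glucose result would be biased or unsound. It would not be; the planned estimate is unbiased under randomization and at worst slightly less precise. The gain for the HbA1c model is about 0-5%, and there is none for the time-by-arm contrast from a main effect in complete data.

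**What to change.** Add one sentence to the Statistical Analysis section, fixed before anyone sees outcomes by arm: the 6-month fasting-glucose regression includes baseline HbA1c as well as baseline glucose and study arm, and a missing baseline HbA1c is replaced by the mean baseline value over both arms combined. Using one value regardless of arm keeps the adjustment independent of assignment and means that no randomized woman leaves the analysis because of this covariate.

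Leave the long-term multilevel model unchanged. Sharpening it would need covariate-by-time terms, which cost more than one degree of freedom. Baseline glucose in the 6-month HbA1c model may be added or omitted, provided that the choice is written down in advance.

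The cost is one sentence and one degree of freedom, with no new visits, samples or participants. Writing it down now also rules out a choice of covariates after the results are known.
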